### **1.6.2 Rationale for increasing the duration of residency of the OxyChip in a tumor**

Patients in the first 2 cohorts of 3 patients in Phase 1A were implanted with the OxyChip for up to 32 days and monitored post explantation. No unacceptable toxicities or unanticipated adverse device effects were observed during or after study procedures. This indicated that the OxyChip is safe and does not elicit any reaction or undesirable effect on the host tissue. Based on these initial results and the need for monitoring patients for longer periods, especially those receiving radiation or chemotherapy treatments, it is desirable to keep the implant for longer periods until the treatment is completed. This is also important if the schedule for surgical resection of the tumor changes after implantation of the chip. We have completed safety and efficacy studies of OxyChips implanted in rat muscle and measured *in vivo* for 52 weeks. The results showed stable and repeated EPR oximetry measurements over the 52-week period without any toxicity or undesirable effects to the host tissue. The chip was intact with stable EPR and oxygen sensitivity. Hence, we requested and received approval for the OxyChip to be implanted in the patients' tumors for up to 52 weeks before removal during routine surgical resection.

### **1.6.3 Rationale for the option of implanting fiducials with the OxyChip**

[figure not shown]
In order to assist with locating the OxyChip during treatment, during EPR measurements, and during/after resection, the protocol was revised to allow for fiducial(s) (either one or two) to be implanted along with the OxyChip during the procedure. The decision to implant fiducials is at the discretion of the investigator.

Because tumors size and shape can change during the course of radiation, the location of the OxyChip in relationship to the tumor may also change. By implanting fiducials with the OxyChip, the location of the OxyChip will be able to be seen on CT scans that patients intermittently receive during radiation treatment as part of clinical care. This will allow for better interpretation of the pO2 measurements that are collected throughout the treatment, as the location of the OxyChip in relation to tumor tissue will be evaluable.

Adding fiducials will also assist in locating the OxyChip for EPR measurements. Although OxyChips can be located *in vivo* using ultrasound guidance, it can be challenging to do so; fiducials can be located quicker than the OxyChip implanted alone and with higher sensitivity. This allows for faster placement of the resonator, which facilitates faster oxygen measurements. This is of great importance in the clinical translation of EPR oximetry, where time is limited.

Fiducials will also assist in procedures during and after resection. In order to assure that the OxyChip has been explanted, the pathology specimen will be scanned prior to surgical closure in the pathology lab. If the implanted fiducial(s) are located in the resected specimen, then there is high confidence that the OxyChip has been successfully explanted (See section 5.2.4 for more information on this procedure). Fiducials can also assist with assessing the pathology specimen after resection to ensure that the OxyChip is not cut during the dissection of the specimen, and to rapidly identify the location of the OxyChip in the specimen. If two fiducials are implanted, the orientation of the OxyChip will be known, so the pathologist will cut parallel to the two fiducials in order to not cut the OxyChip in the process.

A study has been completed where an OxyChip was successfully implanted into a phantom with two fiducials on each side of it in a number of different substrates without difficulty. EPR oximetry data in a known oxygen concentration was also collected from the OxyChip with and without fiducials present. These results showed that the presence of the fiducials had no significant effect on the pO2 measurements (Figure 9).

**Figure 9:** Effect of fiducials on OxyChip pO2 measurements. An OxyChip was inserted into a nitrogen flow tube and EPR oximetry was performed (“no markers”). The same experiment was repeated with two fiducials flanking the OxyChip. No significant difference in pO2 was noted, indicating no effect of the present of the fiducials on OxyChip derived pO2 measurements.

The use of fiducials in the radiation oncology clinic is standard of care in a number of malignancies. For example, in order to facilitate image guidance daily during radiotherapy for prostate cancer the radiation oncologist places two to three fiducials into the prostate prior to treatment under ultrasound guidance in the clinic. These fiducials remain in place permanently after treatment. In the OxyChip protocol, the fiducials will be removed.

## 1.7 Risk/Benefits

In this Phase 1 Safety clinical trial, there are no expected benefits to the patients. The benefit is for those patients who have a desire to advance this technology and/or to improve radiotherapy for future patients. Furthermore, the knowledge gained by repeated measurement of tumor oxygen levels, especially during radiotherapy is critical for developing and implementing novel hypoxia-targeting therapies.

The risks are expected to be minimal. As with any implantation, there is a risk of pain, bleeding or infection. We expect this risk to be minimal and not more than the risk of a core needle biopsy, since the implantation procedure is minimally invasive, and performed with a needle insertion. Risks associated with placement beyond the risks associated with placement of the OxyChip itself are expected to be minimal. There is a very low risk of fiducial migration, estimated at 0.35% in one study of prostate cancer and fiducial placement. Over 1000 fiducials have been implanted into patients in the Radiation Oncology clinic at DHMC as part of routine clinical care for prostate cancer with no significant complications ([name], personal communication). Patients are consented for placement of fiducials in addition to the OxyChip. There is an unknown risk from LiNc-BuO in humans; however, no toxicity is expected based on studies using animal models and because the LiNc-BuO crystals are embedded in biocompatible PDMS to further eliminate any potential risk. Furthermore, the biocompatibility of OxyChips has been established in pre-clinical studies for

up to 52 weeks and, to date, in humans for up to 141 days with approval to be implanted for up to 52 weeks. In addition, the OxyChips will be placed in superficial locations and will be removed in this protocol when the tumor is resected. There is a possibility that the patient might be in an uncomfortable position during oxygen measurements, but re-positioning can be performed at any time if needed.

The study population will consist of patients who are  $\geq 18$  years of age, both genders, and must be competent to consent to participate in the trial. Risks of the device will be minimized by placement of the device under sterile conditions using a minimally-invasive procedure. The implantation site will be monitored closely.

## 2 Study Objectives

### 2.1 Primary Objective

This is a safety study to demonstrate that the implantation procedure, the OxyChip, and any subsequent oxygen measurements will be well-tolerated by the patient with minimal risk for complications. Specific adverse effects that will be monitored include:

- Allergic reactions or signs of inflammation at the site of implantation or systemically
- Infection at the site of implantation
- Bleeding at the site of implantation
- All tumors will be excised with the OxyChip in place, and histology will be analyzed for signs of tissue reaction and inflammation adjacent to the OxyChip
- Device (PDMS-embedded) breakage, loss of EPR or oxygen sensitivity, or change of calibration
- Erosion of skin over the implantation site
- Any unanticipated adverse device effects (UADE) will be assessed and reported. UADE will be defined as, “any serious adverse effect on health or safety or any life-threatening problem or death caused by, or associated with, a device, if that effect, problem, or death was not previously identified in nature, severity, or degree of incidence in the investigational plan or application, or any other unanticipated serious problem associated with a device that relates to the rights, safety, or welfare of subjects” (21 CFR 812.3(s)).

### 2.2 Secondary Objective

This study will also determine the feasibility of repeated measurements of oxygen in tumors using the OxyChip and EPR oximetry. This objective is unrelated to the primary safety objective.

- To assess the feasibility of making repeated measurements of tumor oxygen levels in patients with easily-accessible, superficial tumors.
- To determine the tumor oxygen levels in patients without therapy prior to surgical excision (Phase 1A), or during a course of radiotherapy or neoadjuvant chemotherapy prior to surgical excision (Phase 1B).
- To determine the workflow and time required for each daily oxygen measurement.

### 2.3 Exploratory Objective

Collection and future use of tumor tissue surrounding the implanted device will be done to analyze molecular biomarkers related to hypoxia, angiogenesis, and tumor growth. The tissue analysis will explore the potential for any identifying biomarkers of the tumor that predict or otherwise are associated with variation in tumor growth or responsiveness to therapy.

## 3 Study Design

### 3.1 General Design

This is a Phase 1 clinical trial. Total enrollment will be 60 evaluable patients. Evaluable patients will be defined as patients who have the OxyChip implantation for the minimum of 3 days.

The study is split into Phase 1A (shorter duration of implantation with no other cancer therapy planned prior to excision) and Phase 1B (longer duration of implantation that is typically up to 12 weeks while receiving radiation therapy or longer if receiving neoadjuvant chemotherapy prior to surgical excision), as described below. OxyChip implant duration for both phases can be extended to 52 weeks (excluding the initial 6 evaluable patients in Phase 1A which may have the OxyChip implanted up to 4 weeks).

[figure not shown]
The initial 6 evaluable patients in Phase 1A will have the OxyChip placed for a short duration (up to 4 weeks) after which the OxyChip will be removed when the tumor mass is resected, prior to delivery of any further therapies. After successful implantation and removal of the OxyChip without any unacceptable toxicity in the first 6 evaluable patients, the Phase 1A cohort will be expanded to a total of 30 patients. In order to complete the safety and toxicity assessment of the short-term implantations, we will require that at least 3 patients have OxyChip implantations for a duration of at least 2 weeks, prior to proceeding to Phase 1B (long term implantation). This may require enrollment of additional patients in Phase 1A in order to meet this criterion. Phase 1B will consist of one cohort of 3 evaluable patients receiving chemotherapy treatment and one cohort of 3 evaluable patients receiving radiotherapy. Only after a full evaluation of the first 3 patients that underwent chemotherapy will additional patients receiving chemotherapy be enrolled. Similarly, only after a full evaluation of the first 3 patients that underwent radiotherapy will additional patients receiving radiotherapy be enrolled. The two cohorts of 3 patients in Phase 1B are independent of each other, so either of these cohorts may continue accrual after the initial 3 patients while the other is still accruing for the initial 3 patients. A total of 30 patients will be enrolled in Phase 1B. .

This larger cohort will allow further assessment of safety, as well as optimization of procedures for the OxyChip placement and subsequent oxygen measurements for different tumor types in different anatomical locations. This expanded Phase 1 study will also achieve a secondary goal of increasing patient numbers for specific tumor types (*i.e.*, melanomas, squamous cell carcinomas and sarcomas) to assess the levels of tumor oxygenation and their response to supplemental oxygen breathing.

The phase 1B patients will have up to five oxygen measurements per week during the course of radiation or chemotherapy. Patients will be evaluated weekly during radiotherapy or prior to each chemotherapy administration or follow-up appointment for assessment of any adverse effects, as per the primary objective. Oximetry measurements will be taken periodically, from at least one day after implantation up to the OxyChip's removal. The OxyChip will be removed at a planned surgery as part of standard-of-care therapy. Phase 1A patients will be evaluated at least monthly prior to OxyChip removal for assessment of adverse effects, again for the primary objective.

If a patient cannot or does not return for an evaluation, the study team will contact the patient by phone or email to check for development of new adverse events or changes in health status. Assessments by non-study physicians or physician extenders as part of standard care are also an acceptable replacement, if the patient is not accessible for an in-person evaluation. Following resection, the tissue surrounding the OxyChip will be examined for any adverse effects, as per the primary objective. For the exploratory objectives, the tissue will also be examined for biomarkers associated with hypoxia or growth.

Schema:

PHASE 1A	
Purpose	
Primary: Safety of the OxyChip placement procedure and OxyChip removal after short duration (typically less than 4 weeks, but up to 52 weeks).
 
Secondary: Feasibility of taking repeated oxygen measurements using the OxyChip.

Patient population	
There will be a total of 30 patients enrolled in Phase 1A.
 
Initially, 3 patients will be enrolled; the OxyChip will be placed; physical examination of the site will be made periodically (at least in conjunction with visits where oxygen measurements will be made) starting from one day following implantation for up to 52 weeks – at which point the tumor will be resected with concurrent removal of the OxyChip. If no adverse events are noted in the physical exams or tissue pathology, an additional 3 patients will be enrolled in this phase of the study. The decision to start the second cohort of 3 will be made by the study PI after review of surgical pathology reports and after the first 3 evaluable patients are at a time point more than 2 weeks following surgical removal of the OxyChip. Next, if no unacceptable toxicity is noted after completion of the first 6 patients, the enrollment will be open to 24 more, for a total of 30 patients. (Note: the enrollment totals will include patients enrolled at DHMC or Emory University, once the addition of Emory as a participating site is approved.)
 
In addition the following eligibility and exclusion criteria will apply:
 
 
• Superficial tumors located <math>\leq 3</math> cm from skin or mucosal surface.
 
• Surgical resection of the tumor is planned at least 3 days following implantation.
 
• Eligible tumors for this phase of the protocol are any tumors that (a) are identified by imaging or physical exam to be superficial enough for OxyChip placement and (b) will receive surgical resection with intent to remove the entire tumor.
 

	
 
• Previous radiation to the site is not allowed.
 
• Planned use of chemotherapy or radiation therapy or use of angiogenesis inhibitor prior to resection is not allowed.
 
• Patients do not have to agree to an oxygen measurement in order to be eligible. Although oxygen measurements are desirable, the primary endpoint is safety of the OxyChip placement and removal over a short time frame.
 
• Tumors must be <math>\geq 2.5</math> cm in minimum diameter to be eligible.
 

OxyChip placement	Placement of OxyChip will be through a minimally invasive procedure (see methods for implantation protocol ).
OxyChip removal	The OxyChip will be removed at the time of surgical resection, which will occur within 52 weeks from the time of implantation. Surgery date must be at least three days after placement of the OxyChip. Tumor tissue surrounding the implanted device will be collected and examined for adverse events (primary) and stored to allow for future evaluation of molecular biomarkers (exploratory).
Oxygen measurements	The goal is for at least 2 oxygen measurements to be taken in the period between the day of OxyChip placement and removal (secondary objective). Note, however, that oxygen measurements are not necessary to determine the presence or absence of any unexpected adverse device events of implanting the OxyChip, for the study's primary goal.

PHASE 1B	
Purpose	
Primary: Safety of the OxyChip during neoadjuvant radiotherapy or neoadjuvant chemotherapy with planned surgical resection as part of standard oncologic therapy.
 
Secondary: Feasibility of oxygen measurements during neoadjuvant radiotherapy or neoadjuvant chemotherapy using the OxyChip.

Patient population	
There will be a total of 30 patients enrolled in Phase 1B.
 
Phase 1B will consist of one cohort of 3 evaluable patients receiving chemotherapy treatment and one cohort of 3 evaluable patients receiving radiotherapy. Only after a full evaluation of the first 3 patients that underwent chemotherapy will additional patients receiving chemotherapy be enrolled. Similarly, only after a full evaluation of the first 3 patients that underwent radiotherapy will additional patients receiving radiotherapy be enrolled. The decision to enroll additional patients in each cohort will be made by the study PI after review of surgical pathology reports and after the 3 evaluable patients are greater than 2 weeks after surgical removal of the OxyChip. The two cohorts of 3 patients in Phase 1B are independent of each other, so either of these cohorts may continue accrual after the initial 3 patients while the other is still accruing for the initial 3 patients.
 
In addition, the following eligibility and exclusion criteria will apply:
 
 
• If a patient is to receive neoadjuvant chemotherapy or radiotherapy at a hospital other than DH prior to resection of the cancer at DH, patients
 

	
will still be eligible for enrollment as long as a PI or Co-PI on the study can evaluate the implanted site at least every two weeks during treatment. Of note, patients must receive their surgery at DH to be eligible.
 
 
• Superficial tumors located <math>\leq 3</math> cm from skin or mucosal surface, where neoadjuvant radiotherapy or neoadjuvant chemotherapy followed by surgical resection is planned.
 
• Eligible tumor histology for this protocol is any biopsy proven malignancy expected to undergo neoadjuvant chemotherapy or radiotherapy prior to resection
 
• Previous radiation to the site is not allowed.
 
• Use of angiogenesis inhibitors is not allowed.
 
• Planned use of concurrent neoadjuvant chemoradiotherapy, or sequential neoadjuvant radiation therapy and chemotherapy, prior to resection, is not allowed.
 
• Patients do not have to agree to an oxygen measurement in order to be eligible. Although oxygen measurements are desirable, the primary endpoint is safety of OxyChip during neoadjuvant radiation or chemotherapy.
 
• Tumors must be <math>\geq 2.5</math> cm in minimum diameter to be eligible.
 

OxyChip placement	Placement of OxyChip will be through a minimally invasive procedure ( see methods for implantation protocol ).
OxyChip removal	The OxyChip will be removed with the tumor mass at the time of surgical resection and examined for adverse events (primary goal). Tumor tissue surrounding the implanted device will be collected and stored to allow for future evaluation of molecular biomarkers (exploratory goal).
Oxygen measurements	The goal is at least two measurements prior to the start of radiation therapy and then up to five times per week during radiotherapy or chemotherapy for the secondary objective. Note, however, that oxygen measurements are not necessary for the study's primary goal to determine the presence or absence of any adverse events after implantation of the OxyChip.

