## Study Summary

Title	A Single-Institutional, Phase I Trial of Repeated Oxygen Measurements in Subcutaneous Tumors by Electron Paramagnetic Resonance (EPR) Oximetry using an Implantable Oxygen Sensor (OxyChip)
Short Title	EPR Oximetry using OxyChip
Protocol Number	D14007, CPHS 28499
Phase	First-in-humans, early feasibility study for OxyChip implantation with subsequent expansion to a larger Phase I trial. Phases: 1A (tumor with planned surgical resection only and consequently with an expected duration of implantation for up to 4 weeks); and 1B (tumor with neoadjuvant radiation therapy or chemotherapy followed by planned surgical resection, with expected duration of implantation of up to 12 weeks for radiation and 24 weeks or more for chemotherapy.) OxyChip implant duration for both phases can be extended to 52 weeks excluding the first 6 patients enrolled into Phase 1A where implant duration is up to 4 weeks.
Methodology	Phase I (first-in-human, early feasibility trial)
Study Duration	5 years
Study Center(s)	Single institution: Dartmouth-Hitchcock Medical Center (DHMC)
Objectives	Primary: Establishment of safety of OxyChip implantation in humans; Secondary: establishment of feasibility of OxyChip for measurements of oxygen using EPR oximetry in humans.
Number of Subjects	60 total evaluable subjects planned: 3 subjects in Phase1A will be evaluated and reviewed before enrolling another 3 subjects. After completion of the first 6 subjects in Phase 1A, if there are no unacceptable toxicities from the OxyChip, that cohort will be expanded to a total of 30 subjects. Phase 1B will consist of one cohort of 3 subjects receiving chemotherapy and one cohort of 3 subjects receiving radiotherapy. Once a cohort has enrolled 3 subjects and there are no unacceptable toxicities from the OxyChip, the completed cohort will be expanded to enroll additional subjects. No more than 30 subjects will be enrolled in Phase 1B. Phase 1A and Phase 1B will be evaluated separately with regards to this expansion; i.e. , Phase 1A may expand to 30 subjects while Phase 1B is still accruing.
Diagnosis and Main Inclusion Criteria	Tumors, located within 3 cm of skin or mucosal surface AND tumor resection is planned.

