#### 5.2.4 OxyChip and Fiducial removal

The OxyChip and fiducial(s) will be excised with the surgical specimen. The surgeon determines the timing of surgery, but it will typically be planned to be within 4 weeks for Phase 1A, or after completion of radiotherapy or chemotherapy for Phase 1B, although the OxyChip may remain implanted for up to 52 weeks for both Phases (excluding the first 6 patients enrolled into Phase 1A). The minimum time from implantation to surgical excision required for inclusion is 3 days. Note, patients in Phase 1B are expected to have the OxyChip in place for a minimum of 5 weeks (the expected duration of radiation therapy). The protocol and goals for removal will be as follows:

- (i) All attempts will be made to maintain the OxyChip in the tissue specimen, without disrupting the shape or position within the tumor mass.
- (ii) In collaboration with the surgeon, after the patient has been anesthetized, imaging of the fiducial(s) will occur prior to surgery in order to identify the putative location of the OxyChip and facilitate surgical removal.
  - a. We anticipate the fluoroscopy will be sufficient for identification of the fiducial prior to surgical removal (and after). However, due to concerns that more advanced imaging may be necessary, the first three patients with fiducial implantation will have their surgery performed at DHMC in the Center for Surgical Innovation (CSI). If fluoroscopy is sufficient for identification, then subsequent surgeries can be performed in standard operating rooms as desired if fluoroscopy is available for identification of fiducials before and after surgery.
    - i. In the first three patients in the CSI, if the fiducial is not found prior to surgery either CT or MRI imaging will be performed to identify the fiducials. If the fiducials are found within the expected surgical field, or reasonably adjacent, fiducials will be removed during surgery. If the fiducials are found in an unanticipated area, consultation between the PI and the surgeon will occur as to whether surgical resection is acceptable. All decisions regarding surgery will be at the discretion of the surgeon. If no fiducials are found after advanced imaging prior to surgery, then surgery will proceed as planned as all reasonable measures will have been taken to identify the location of the OxyChip at that time.

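### The Phase 1B expansion decisions count patients by 3 days of implantation, with no minimum radiotherapy or chemotherapy received while the chip is in place

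*Combined protocol and SAP*

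**What the plan says.** The definition in section 3.1 is trial-wide and refers only to time in place: "Evaluable patients will be defined as patients who have the OxyChip implantation for the minimum of 3 days". Section 7.2 uses the same set for the primary and secondary analyses.

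The Phase 1B cohorts are counted in that unit: "Phase 1B will consist of one cohort of 3 evaluable patients receiving chemotherapy treatment and one cohort of 3 evaluable patients receiving radiotherapy". Expansion of the chemotherapy arm is conditioned as follows: "Only after a full evaluation of the first 3 patients that underwent chemotherapy will additional patients receiving chemotherapy be enrolled". The radiotherapy text is parallel. The Phase 1B schema leaves the decision with the principal investigator and fixes its timing: "after review of surgical pathology reports and after the 3 evaluable patients are greater than 2 weeks after surgical removal of the OxyChip". Phase 1B has this stated purpose: "Safety of the OxyChip during neoadjuvant radiotherapy or neoadjuvant chemotherapy with planned surgical resection".

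On residence, section 5.2.4 says that "patients in Phase 1B are expected to have the OxyChip in place for a minimum of 5 weeks (the expected duration of radiation therapy", and it plans removal once therapy is complete. The Study Summary ties Phase 1B implant time to the therapy course and expects up to 12 weeks with radiation and 24 weeks or more with chemotherapy.

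Earlier in the sequence section 3.1 does set a duration floor: "we will require that at least 3 patients have OxyChip implantations for a duration of at least 2 weeks, prior to proceeding to Phase 1B". Section 4.4.1 allows the chip to be taken out early, including at the patient's request.

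The Study Summary describes the expansion step differently: "Once a cohort has enrolled 3 subjects and there are no unacceptable toxicities from the OxyChip, the completed cohort will be expanded".

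**The concern.** Phase 1B asks whether the chip is safe while the tumour is being irradiated or the patient is on chemotherapy. The expansion decision should therefore rest on patients who had a meaningful amount of that therapy with the chip in place. The unit counted does not ensure this. It measures days since implantation, it is the unit that also serves Phase 1A, and it makes no reference to therapy. The waiting period before the decision runs from removal, so it does not make up for short exposure beforehand.

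A patient who starts therapy, has the chip removed early or stops treatment, and has passed day 3 fills one of three places in full. No section replaces that patient. With only three places, one such patient removes a third of the intended information. If it happens, an arm can be described as cleared when the combination of chip and therapy was only lightly tested at that point.

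**Working it through.** **1. Is there a figure to reproduce?** No. Section 7.1 says that moving between cohorts does not rest on statistical significance, and the protocol gives no event rate, error rate or operating characteristic for these decisions. The enrolment arithmetic is consistent: 6 + 24 = 30 in Phase 1A, 30 + 30 = 60 overall, and 30 − 6 = 24 Phase 1B patients after the two initial cohorts.

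**2. What each provision requires by way of therapy exposure**

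| Provision | What it requires | Minimum therapy with chip in place |
|---|---|---|
| Evaluable (3.1) | 3 days implanted | none |
| Eligibility (4.1) | at least 3 days anticipated to excision | none |
| First three per arm (3.1) | evaluable, and had the therapy | some, amount not stated |
| Full evaluation (3.1) | not defined | none |
| PI decision (3.1 schema) | pathology read, more than 2 weeks after removal | none |
| Residence (5.2.4, Study Summary) | an expectation | not a condition for counting |
| Early removal (4.4.1) | permitted | no replacement rule |
| Entry to Phase 1B (3.1) | at least three patients with at least 2 weeks | not applicable (no therapy in Phase 1A) |

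The wording that patients received or underwent the therapy rules out someone with no therapy at all. It does not rule out someone with very little.

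**3. Size of the gap in days**

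- Against the expected 5-week minimum: 3/35 = 8.6%.
- Against 12 weeks: 3/84 = 3.6%.
- Against 24 weeks: 3/168 = 1.8%.
- The 2-week floor used to enter Phase 1B is 14/3 = 4.7 times the 3-day threshold.
- Three days is shorter than the weekly interval between assessments during radiotherapy (sections 3.1 and 6.3). Because two measurements are sought before radiotherapy starts (3.1 schema), early implant days may precede the first fraction.

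Worst-case bound: three patients at the threshold give 3 × 3 = 9 patient-days. The comparison is 3 × 35 = 105 at the expected 5-week minimum, or 3 × 168 = 504 at 24 weeks.

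**4. What short exposure does to a three-patient check (illustration only)**

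Assumptions, none of them in the protocol: a full-course event probability p between 0.1 and 0.5, a constant hazard, and a 35-day course. The event probability over 3 days is then q = 1 − (1 − p)^(3/35). The probability of seeing no event is (1 − p)³ with three full courses, (1 − p)²(1 − q) if one of the three has only 3 days, and (1 − q)³ if all three do.

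| p | three full courses | one of three short | all three short |
|---|---|---|---|
| 0.1 | 0.729 | 0.803 | 0.973 |
| 0.2 | 0.512 | 0.628 | 0.944 |
| 0.3 | 0.343 | 0.475 | 0.912 |
| 0.4 | 0.216 | 0.345 | 0.877 |
| 0.5 | 0.125 | 0.236 | 0.837 |

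The middle column is the more realistic one. At p = 0.3 a single short-exposure patient raises the chance of an event-free check from 0.343 to 0.475.

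**The case against.** The strongest reply is that Phase 1B residence is set by the therapy course. The Study Summary and section 5.2.4 both link removal to completing therapy, and early removal under section 4.4.1 needs a surgical procedure. The 2-week floor was needed in Phase 1A because surgical scheduling alone sets residence there. On this view short exposure will be uncommon, and the PI, with pathology in hand, would notice it. This stands as a statement about frequency. It does not supply a rule for the patient who does come out early, and with three places one such patient matters.

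A reader might infer several stronger things, which the documents do not support:

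- *That this decision is the only safety check.* Section 8.4 stops the study for any grade 3 or higher toxicity, patients are assessed weekly or before each chemotherapy administration (section 6.3), and the monitoring committee meets quarterly and can suspend (section 10.1). All of these run whatever the evaluability rule says. None of them requires therapy exposure before expansion.
- *That expansion would proceed with no human data on longer implantation.* Section 1.7 reports human residence up to 141 days, and section 1.5.5 says the FDA's Phase 1 requirement has been met. The enrolment detail in section 1.5.1 was not in the text available to me, so I cannot tell whether the Phase 1B cohorts had already been cleared, or on what exposure.
- *That 9 patient-days is what to expect.* It needs all three patients to be explanted at about day 3 after starting therapy.

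The constant-hazard illustration can also be challenged. Bleeding and infection (section 2.1) may occur soon after implantation, in which case it exaggerates what short exposure loses.

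Finally, requiring the entire planned course would be too strict, since it would discard a patient explanted at 90% of it. That is a fair limit on the remedy.

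**Conclusion.** The gap is real and lies in the rule; nothing in the documents shows that an arm was expanded this way. The unit counted for Phase 1B expansion is 3 days of implantation, no section sets a minimum therapy exposure with the chip in place, and a patient with early removal or stopped therapy counts in full. Up to 24 later Phase 1B patients across both arms depend on these decisions.

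The likely size is one weakly informative patient among three. The ratios of 9 to 105 or 504 patient-days are an outer bound, and the probabilities depend on assumed event rates and a constant hazard. The conclusion itself needs neither. It rests on the text, and on the protocol's own decision to set a duration floor one step earlier.

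The change is worth making because it is cheap and makes the expansion decision answer the question Phase 1B was set up to ask. If the initial cohorts are already complete, the value lies mainly in how their clearance is reported.

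**What to change.** 1. Keep the 3-day definition for the overall safety analysis set.
2. In section 3.1 and the Phase 1B schema, add a separate definition of who counts toward the first three in each arm. Base it on a minimum amount of radiotherapy or chemotherapy received with the chip in place. The sponsor sets the level; a stated fraction of the planned course would do and need not be all of it.
3. Always count a patient whose chip is removed early for an event possibly related to the device or a study procedure. To limit dependence on attribution, apply the convention in section 8.3.1.3, which treats causality of questionable relationship as associated.
4. Replace other patients who fall short, for this count only. Their data stay in the safety analysis.
5. Define the full evaluation, and report therapy exposure with the chip in place for each of the first three patients in each arm.
6. Reconcile the Study Summary, which refers to three enrolled subjects, with the schema, which refers to evaluable patients, pathology review and more than 2 weeks after removal.

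Cost: protocol wording, with no new procedures. Expansion may open later, possibly by months in the chemotherapy cohort, since replacing one patient there could add 24 weeks or more at the expected residence.
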